7.6 Definition of Secondary Outcome Measures

7.6.1 Secondary Implementation Outcomes

1. Fidelity to the Critical Action Checklist relating to the provision of ED-initiated BUP with referral for ongoing MAT as captured by the CAC form. For the binary variable, if all critical actions were completed for a given participant the variable will be coded 1 versus 0 if at least one critical action was not completed. The count variable will be defined as the number of critical actions completed per given participant.
2. Rates of enrolled patients with OUD receiving an appointment for opioid treatment provider/program upon ED discharge as recorded on EDR form. The variable will be coded 1 if YES is endorsed on “Did the patient receive a referral to opioid use disorder (OUD) treatment?” and 0 if the answer is NO.
3. Number of ED providers receiving DATA 2000 training as reported on ICH form: The outcome is the number of participants who endorsed YES on the question “In the past year, did you attend or complete a DATA 2000 training on buprenorphine prescribing that would allow you to obtain a DEA waiver?”.
4. Number of clinicians providing ED-initiated BUP with referral for ongoing MAT as reported in ICH form.
5. ED provider readiness and preparedness ruler scores to initiate BUP and provide referral for ongoing MAT as reported on RRL form: The outcome will be scored from the following

questions: “On a scale from 0 to 10, how prepared are you to provide ED-initiated buprenorphine with referral for ongoing medication assisted treatment (MAT) for the treatment of opioid use disorder, where 0 equals “not prepared at all” and 10 equals “totally prepared?” and “On a scale from 0 to 10, how ready are you to provide ED-initiated buprenorphine with referral for ongoing MAT for the treatment of opioid use disorder, where 0 equals “not ready at all” and 10 equals “totally ready?”.

6. ED ORCA scores relating to ED-initiated BUP with referral for ongoing MAT (OE1 and OE2 form). The score will be dichotomized, as was done in Hawk et al.⁵, where scores in the first four quintiles were categorized as less ready, and scores in the upper quintile is considered most ready.
7. Community opioid treatment provider/program readiness and preparedness ruler scores to continue MAT for patients with OUD who have received ED-initiated BUP (RRL form).
8. Community opioid treatment provider/program ORCA scores relating to receiving patients with OUD who have received ED-initiated BUP (OC1 and OC2 form).

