4.3.2 Implementation Hypotheses

1. There will be higher fidelity to the critical action checklist relating to the provision of ED-initiated BUP with referral for ongoing MAT in the IF evaluation period compared with the baseline evaluation period
2. A greater rate of patients in the IF evaluation period will receive an appointment with an opioid provider/program upon ED discharge compared with the baseline evaluation period
3. A greater number of providers will undergo DATA 2000 training in the IF evaluation period compared with the baseline evaluation period
4. A greater number of clinicians will provide ED-initiated BUP with referral for ongoing MAT in the IF evaluation period compared with the baseline evaluation period
5. ED provider readiness and preparedness ruler scores will reflect a greater readiness and preparedness for provision of BUP and referral for ongoing MAT in the IF evaluation period compared with the baseline evaluation period
6. ED ORCA scores will reflect a greater organizational readiness to change with respect to provision of ED-initiated BUP in the IF evaluation period compared with the baseline evaluation period
7. Community opioid treatment provider/program provider readiness and preparedness ruler scores to continue MAT for patients with OUD who have received ED-initiated BUP will be greater in the IF evaluation period compared with the baseline evaluation period
8. Community opioid treatment provider/program ORCA scores relating to receiving patients with OUD who have received ED-initiated BUP will be greater in the IF evaluation period compared with the baseline evaluation period.

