8.3 Secondary Implementation Outcome Measures

To compare the baseline evaluation and IF evaluation periods on:

1. Provider fidelity to a critical action checklist relating to the provision of ED-initiated BUP with referral for ongoing MAT

2. Rates of enrolled patients receiving an appointment for opioid treatment provider/program upon ED discharge
3. Number of ED providers receiving DATA 2000 training
4. Number of clinicians providing ED-initiated BUP with referral for ongoing MAT
5. ED provider readiness and preparedness ruler scores to initiate BUP and provide referral for ongoing MAT
6. ED Organizational Readiness to Change Assessment (ORCA) scores¹¹ relating to ED-initiated BUP with referral for ongoing MAT
7. Community opioid treatment provider/program readiness and preparedness ruler scores to continue MAT for patients with OUD who have received ED-initiated BUP
8. Community opioid treatment provider/program Organizational Readiness to Change Assessment (ORCA) scores relating to receiving patients with OUD who have received ED-initiated BUP

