11.8 Administration of BUP During IF Evaluation Period

The following procedures will be incorporated into the training of ED providers during the IF period. We will assess fidelity to the procedures (adherence) using a critical action checklist. The checklist will include confirmation of documentation of: urine toxicology and liver function tests obtained; patient participant meets criteria for DSM-5 moderate-severe opioid use disorder; urine positive for opioid; formal assessment of Clinical Opioid Withdrawal Scale (COWS); ED-initiated BUP provided; BUP education and induction instructions provided; and referral for ongoing medication assisted treatment. Education regarding BUP and Induction is provided; and Appointment for ongoing MAT provided. Providers will be instructed to induce patients onto BUP using an induction and stabilization protocol that has been well tolerated by patients in our previous study.⁷ Buprenorphine induction will take place in the ED or unobserved, and should be based on the study patient's level of opioid withdrawal as measured by the COWS. Depending on the study patient's level of physical dependence, the goal of the induction will be 8mg on the first day and 16mg on subsequent days. Study patients will receive a dose in the ED if they exhibit moderate to severe withdrawal on the COWS and will leave with a prescription for the daily doses needed prior to their scheduled follow-up appointment, and their significant others, will be provided with instructions for unobserved induction if their COWS score indicates less than mild withdrawal (Mild 5-12) at the time of the ED visit. Unobserved induction has become common practice⁵⁰ and was used successfully in our prior study of ED-initiated BUP. Unobserved induction will also have a goal of 8mg on the first day. In an effort to maximize retention and abstinence achievement during the induction we will instruct ED providers to provide study patients with a scheduled appointment for follow up with an office-based BUP provider or an OTP within 96 hours of their ED visit.

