7.0 IMPLEMENTATION AND EFFECTIVENESS ANALYSIS

7.1 Definition of Primary Implementation Outcome Measure

The primary outcome is the rate of provision of ED-initiated BUP with referral for ongoing MAT. The rates of provision of ED-initiated BUP with referral for ongoing MAT will be based on:

1. Proportion of enrolled patients who receive ED-initiated BUP with referral for ongoing MAT or
2. Computed from ED data on the numbers of providers and their patients who received ED-initiated BUP with referral for ongoing MAT. As estimating a very low frequency outcome by sampling is not reliable, computation will be used if (1) results in zeros or small ratios. This entails reviewing existing ED records and counting the number of ED providers assigned to patients with OUD, and the number of patients who received ED-initiated BUP with referral for ongoing MAT during the study period.

Note that subsequent sections of this SAP indicate that there are statistical methodologies (a Bayesian approach and a ChangeToOne approach) that can be implemented to handle low frequency outcome. Thus, for the primary analysis the primary implementation outcome will be defined as in (1). A participant will be counted as having received ED-initiated BUP with referral for ongoing MAT if there is evidence that they were administered, prescribed, or provided BUP for take home administration. Further, there must also be evidence that the participant received a referral for opioid use disorder treatment. The primary implementation outcome measure will be scored from the ED Visit Review (EDR) form based on the following two questions:

- Were any of the following medications administered in the ED, prescribed at discharge, and/or given a take home dose?
- Did the patient receive a referral to opioid use disorder (OUD) treatment?

The outcome measure is calculated as an indicator that both of the following are true:

- BUP was administered in the ED, prescribed and/or provided for take home administration (i.e., ERBUPMED='1' or ERBUPRX='1' or ERBUPTH='1').
- Referral made for OUD treatment (i.e., EROPIREF='1')

If either of these criteria are met and the other missing, then the primary outcome measure will be missing. Since the data arise from the electronic health record, missing data should be exceedingly rare.

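### The secondary outcome named as receipt of an appointment is scored from the referral question, so it measures referral and repeats a required component of the primary outcome

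*SAP*

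**What the plan says.** Protocol 8.3 lists the second secondary implementation outcome as "Rates of enrolled patients receiving an appointment for opioid treatment provider/program upon ED discharge". The matching hypothesis in Protocol 4.3.2 is that more patients in the IF evaluation period "will receive an appointment with an opioid provider/program upon ED discharge". Protocol 12.14.3 analyses this outcome with the primary model.

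SAP 7.6.1 item 2 keeps the name: "Rates of enrolled patients with OUD receiving an appointment for opioid treatment provider/program upon ED discharge as recorded on EDR form". The scoring rule that follows is: "The variable will be coded 1 if YES is endorsed on" the question "Did the patient receive a referral to opioid use disorder (OUD) treatment", and 0 if the answer is NO.

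SAP 7.1 uses the same EDR question to score the primary implementation outcome. A primary success needs BUP administered, prescribed or given to take home, and also a referral (EROPIREF='1').

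On appointments themselves, Protocol 11.8 says ED providers will be told to "provide study patients with a scheduled appointment for follow up with an office-based BUP provider or an OTP within 96 hours" of the ED visit. SAP 2.3.2.2 repeats this.

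**The concern.** The named outcome and the scored item are different things. A referral can be made with or without a booked visit, and neither document says that one counts as the other. Under the rule as written, a referral rate would be reported under an appointment label, and the protocol's appointment hypothesis would go untested while appearing to be tested.

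There is a second consequence. SAP 9.0 allows secondary findings to be reported as noteworthy when their p-values are well below 0.05. A small p-value here could be read as support for the primary result from a different measure, although the item is already inside the primary outcome.

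**Working it through.** The plan states no figure for this outcome, so the check is one of definitions.

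**1. What is scored.** Write B for any of the three BUP fields in SAP 7.1 (ERBUPMED, ERBUPRX, ERBUPTH) being 1, R for YES on the EDR referral question, and A for a scheduled appointment.
- Outcome as named (Protocol 8.3, SAP 7.6.1): A.
- Outcome as coded (SAP 7.6.1 item 2): R.
- Primary implementation outcome (SAP 7.1): B and R.

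A does not enter the coding anywhere.

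**2. Overlap with the primary outcome.** Since (B and R) implies R, each primary success is a success on the coded secondary outcome. SAP 3.1.3 assigns both to the same ITT population, so the secondary rate can never be below the primary rate. For example, at the 25% hypothesised for the IF evaluation period in Protocol Table 3, at least 25% of patients would be counted as having an appointment, whatever was booked. The coded variable also matches the referral row already present in the SAP Table 13 shell, beside the primary outcome.

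**3. Effect on the between-period contrast.** Assume that every appointment is also recorded as a referral. Then

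rate(R) = rate(A) + rate(R without A),

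and therefore

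change in R = change in A + change in (R without A).

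The error in the IF effect is the last term. Its sign depends on how the share of referrals without an appointment moves between periods, and the documents give no rate for either. The pairs below are assumed and only show the range:

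| Referral, baseline to IF | Appointments, baseline to IF | Coded change | Change in appointments |
|---|---|---|---|
| 60% to 80% | 10% to 50% | +20 points | +40 points |
| 50% to 80% | 20% to 50% | +30 points | +30 points |
| 60% to 80% | 10% to 10% | +20 points | 0 points |

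The coded outcome can understate, match or overstate the change in appointments.

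**4. Ceiling.** If baseline referral is r, the coded outcome can rise by at most 1 - r. With an assumed r of 80%, that is 100% - 80% = 20 points. Protocol 3.1 describes referral as usual ED practice and Protocol 11.9 leaves baseline referral to existing site practice, so r need not be small. Its value is not given.

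**5. Is there an appointment field?** Protocol 11.8 contains the words "Appointment for ongoing MAT provided", but in a fragment after the sentence listing the checklist content has ended. The descriptions of the checklist in Protocol 10.2.17 and SAP 2.3.1.4 end with referral and list no appointment item. The EDR and CAC forms are not reproduced. Whether a scheduled appointment was recorded cannot be settled from the documents.

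**The case against.** The best defence is that this is a labelling matter. The SAP quotes the scoring question in full, so a careful reader can see what is measured. It is one of eight secondary implementation outcomes, secondary findings are hypothesis-generating (SAP 9.0), and the primary analysis is untouched. The documents also do not always separate the two terms. Protocol 11.9 speaks of referral in both periods, Protocol 6.2 attaches the 96-hour target to referrals, and the fragment in Protocol 11.8 may simply be duplicate wording with one term swapped for the other. A true appointment measure would overlap with referral too.

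This limits the weight of the point but does not remove it. Protocol 11.8 and SAP 2.3.2.2 describe a scheduled visit within a set time, which is more specific than a YES to a referral question. No passage equates the two.

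A reader might infer three stronger things, and none is supported:
- That the coding dilutes the IF effect. No rates are given, and step 3 of the working shows that the direction is open.
- That handing over a referral list was scored as an appointment, mainly at baseline. No passage says that a list scores YES. The only list handout described (Protocol 9.1.1) goes to patients who do not meet the OUD criteria and are not enrolled.
- That the checklist certainly holds an appointment item. Two of its three descriptions omit one.

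**Conclusion.** The scoring rule does not measure the outcome it names. As written, the analysis will report a referral rate, will leave the protocol's appointment hypothesis untested, and will repeat one of the two required components of the primary outcome. One of two components is a statement about the definition, not about the share of events. These conclusions follow from the text alone.

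The size and direction of any distortion of the IF effect are unknown. Only the ceiling of 1 - r and the floor at the primary rate are certain. The primary analysis is not affected. The point deserves correction because it changes what the trial can say about appointments.

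**What to change.** Check the final EDR and CAC forms for a field that records a scheduled appointment. Protocol Table 2 schedules both forms in both evaluation periods, so either could supply the contrast.

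- **If such a field exists:** score SAP 7.6.1 item 2 from it and name the variable.
- **If it does not:** rename the outcome as referral to OUD treatment, state that it is a component of the primary implementation outcome, record the departure from the protocol definition, and draw no conclusion about appointments.

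The SAP (version 2.0, September 2021) postdates the last enrolment date in SAP 3.3.6 (October 2020), so only fields already collected can be used. The first course costs a different source variable and a rerun of one secondary analysis. The second costs a few lines of SAP and report text.

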12.3 Experimental Design

The experimental design will be a modified stepped wedge, as shown in Figure 2. The proposed study will be conducted at 4 ED sites, with a randomized order of when each site starts the protocol. Resource limitations preclude the use of more than 4 sites. At each of the study sites, approximately 25-30 of diverse ED providers will be engaged in the IF activities and evaluation research. The proposed sequence of baseline evaluation, IF and subsequent IF evaluation activities will take approximately 30-33 months at each site. Site selection criteria (e.g., a large prevalence of patients with OUD, population representative of US population, with sufficient referral networks for patients needing formal addiction treatment) will ensure the feasibility of providing the planned implementation research and generalizability of the study findings.

We plan to enroll a minimum of 240 (~120 during both the baseline evaluation period and IF evaluation periods = 240) patients with moderate/severe OUD at each of the 4 study sites, or approximately 960 patients total. The adequacy of this sample size to grant sufficient power for the two alternative hypotheses is discussed below. Enrollment will be monitored to ensure balance between the two enrollment periods at each site.

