FSR	Final Study Report
IF	Implementation Facilitation
IFEP	Implementation Facilitation Evaluation Period
ICC	Intra Class Correlation
LN	Lead Node
MAT	Medication-assisted Treatment
NA	Narcotics Anonymous
NIDA	National Institute on Drug Abuse
ORCA	Organizational Readiness to Change Assessment
OUD	Opioid Use Disorder
OTP	Opioid Treatment Program
PARiHS	Promoting Action on Research Implementation in Health Services
PI	Principal Investigator
RA	Research Associate
SAE	Serious Adverse Event
TLFB	Timeline Follow-back
UDS	Urine Drug Screen

LIST OF PATIENT PARTICIPANT eCRFs

Form Code	Form Name
AD1	Adverse Event
AD2	Serious Adverse Event Summary
AD3	Serious Adverse Event Medical Reviewer
CAC	Critical Action Checklist
CCJ	Crime and Criminal Justice
CLG	Contact Log
COM	Communication Log
DEM	Demographics
DM1	Additional Demographics
EC0069B	Enrollment 0069B (Baseline Evaluation)
EC0069C	Enrollment 0069C (IF Evaluation Period)
EC0069P	Enrollment 0069P (Screening)
EDR	ED Visit Review
EDV	ED Visits and Hospitalization
EHQ	ED Health Quiz
EQD	EQ-5D-3L
ESL	ED Daily Screening Log
ETF	Engagement in Treatment: Facility
ETP	Engagement in Treatment: Patient
F69	Timeline Followback Page 2
FLG	Facility Contact Log
FVT	Follow-up Visit Scheduling
HS1	Health Services Utilization Page 1: Inpatient
HS2	Health Services Utilization Page 1: Outpatient
HSI	Health Services Utilization: Inpatient
HSO	Health Services Utilization: Outpatient
HST	Health Status
HVL	Healthcare Visit Logistics
MVF	Missed Visit
NDI	National Death Index

Form Code	Form Name
ODE	Overdose Events
OSU	Other Substance Use
PDR	Protocol Deviation Review
PDV	Protocol Deviation
PES	Patient Eligibility Summary
STC	Study Completion
T69	Timeline Followback Page 1
TAP	TLFB Assessment Period
UDS	Urine Drug Screen

LIST OF PROVIDER PARTICIPANT eCRFs

Form Code	Form Name
D69	Focus Group Demographics
EC0069IB	Enrollment 0069IB (Provider Participant)
FGT	Focus Group Tracking
ICH	Individual Characteristics
OC1	Organizational Readiness to Change Assessment (ORCA) Community
OC2	Organizational Readiness to change Assessment (ORCA+) Community
OE1	Organizational Readiness to Change Assessment (ORCA) ED
OE2	Organizational Readiness to change Assessment (ORCA+) ED
RRL	Readiness Ruler
SC1	Site Characteristics - ED
SC2	Site Characteristics – OTP Page 1
SC3	Site Characteristics – OTP Page 2
SC4	Site Characteristics – OTP Page 3
SC5	Site Characteristics – Community Page 1
SC6	Site Characteristics – Community Page 2
WEL	Introduction

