3.2 Other Populations

3.2.1 Survey Participant Population

The survey population includes all provider participants who were enrolled in the study and who completed at least one IF survey.

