3.3.3 IF Survey Dates

The baseline survey will occur toward the end of the BEP. This will be followed by two more survey visits (Follow-up Survey 1 and Follow-up Survey 2) that will occur at the beginning and toward the end of the IFEP.

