IFEP	N	X.x	X.xx; X.xx
Sex			
Male	N	[ref]	[ref]
Female	N		
Race			
White	N	[ref]	[ref]
Black/African American	N		
Other	N		
Ethnicity			
Not Hispanic/Latino	N	[ref]	[ref]
Hispanic/Latino	N		
Sex-by-study phase interaction ²			
Male	N	X.x	X.xx; X.xx
Female	N	X.x	X.xx; X.xx
Race-by-study phase interaction ²			
White	N	X.x	X.xx; X.xx
Black	N	X.x	X.xx; X.xx
Other	N	X.x	X.xx; X.xx
Ethnicity-by-study phase interaction ²			
Not Hispanic/Latino	N	X.x	X.xx; X.xx
Hispanic/Latino	N	X.x	X.xx; X.xx

¹ Note that only covariates which remained in the final covariate-adjusted model will be included in this table.

² Coefficient and corresponding credible intervals are presented for the intervention effect in a particular subgroup (e.g., males).

Table 20: Summary of MOUD Practices by Site Over Time from EHR-abstracted Data

	Baseline Evaluation Period					IF Evaluation Period				
	MA Johns Hopkins ED	GNY Mount Sinai ED	OV University of Cincinnati ED	PNW Harborview Medical Center ED	Total	MA Johns Hopkins ED	GNY Mount Sinai ED	OV University of Cincinnati ED	PNW Harborview Medical Center ED	Total
Buprenorphine										
Administered	N									
Prescribed	N									
Administered and prescribed	N									
Unique providers administering or prescribing	N									
Naloxone										
Dispensed	N									
Prescribed	N									
Dispensed and prescribed	N									
Unique providers dispensing or prescribing	N									
X-waiver										
Physicians	N									
APPs	N									
Additional staff (counselors/peers)	N									

Table 21: COVID-19 Sensitivity Analyses Results for Primary Implementation Outcome

Sensitivity Analysis	GLMM		Bayesian Analysis		
	Intervention Coefficient	p-value	Risk Difference Estimation Time Point	Risk Difference	95% Credible Interval
Pre-COVID data	X.xx	x.xxx	Mid-point (day 632)	X.xx	X.xx; X.xx
			COVID-19 Pause (day 1423)	X.xx	X.xx; X.xx
COVID pause removed	X.xx	x.xxx	Mid-point (day 632)	X.xx	X.xx; X.xx
			COVID-19 Pause (day 1423)	X.xx	X.xx; X.xx

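### Secondary implementation outcome 4 counts only clinicians who answered a provider survey, with no denominator, so a difference between periods can reflect survey response as well as practice

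*SAP*

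**What the plan says.** SAP 7.6.1, item 4, gives the outcome in one line: "Number of clinicians providing ED-initiated BUP with referral for ongoing MAT as reported in ICH form". It states no question text, recall window, survey wave, coding rule or denominator.

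ICH (Individual Characteristics) appears in the SAP's "LIST OF PROVIDER PARTICIPANT eCRFs", not among the patient or record-abstraction forms. The one ICH question that the SAP prints is in item 3 and is put to the respondent personally: "In the past year, did you attend or complete a DATA 2000 training on buprenorphine prescribing that would allow you to obtain a DEA waiver".

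On who can be counted, SAP 3.2.1 says: "The survey population includes all provider participants who were enrolled in the study and who completed at least one IF survey". On when, SAP 3.3.3 says: "The baseline survey will occur toward the end of the BEP". It places the later waves thus: "Follow-up Survey 1 and Follow-up Survey 2) that will occur at the beginning and toward the end of the IFEP".

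Protocol 12.14.3 compares this outcome between the two evaluation periods with count models. The only offset it mentions is how long the provider has been trained.

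A record-based count is also planned. Under SAP 2.3.1.5 the sites abstract BUP activity from the EHR, and the compiled file has gone to the data and statistics center. SAP Table 20 has a buprenorphine row, "Unique providers administering or prescribing", by site for each evaluation period. SAP 7.7 summarises these data and allows optional exploratory use. It does not link them to item 4.

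**The concern.** The outcome is meant to show how far BUP provision spread among ED clinicians. Protocol 6.4 defines the provider group as every credentialed ED provider able to prescribe BUP. A raw survey count can only show how many respondents reported providing it. It therefore mixes two quantities, adoption and survey participation, and nothing in the definition or the planned model separates them.

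The survey conditions also differ between periods. SAP 2.3.3 says that, apart from the site principal investigator, ED providers were not told of the study's intent or of the IF plan during the BEP. Protocol 11.10 then describes training, champions and individual performance feedback on BUP prescribing during IF. Willingness to answer could plausibly change between waves. If it does, a reported change in the number of providing clinicians could partly or wholly be a change in who returned the form.

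**Working it through.** The documents give no expected count, response rate, effect size or power for this outcome, so there is no figure of the plan's own to reproduce. The check has three parts.

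**1. What the survey count estimates.** Let N be the clinicians surveyed, π the share who truly provided BUP, and r the response rate among those who did, assuming accurate reporting.

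Expected survey count = N × π × r.

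If N and π are the same in both periods:

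IFEP/BEP ratio = (N × π × r_IFEP) / (N × π × r_BEP) = r_IFEP / r_BEP.

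For scale only, take N from the providers per site in Protocol 12.3 ("approximately 25-30 of diverse ED providers will be engaged in the IF activities and evaluation research"): 4 × 25 = 100 to 4 × 30 = 120. This is not a stated survey sample. The shares (20% and 50%) and response rates (40% to 90%) are assumptions.

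| Response BEP / IFEP | N = 100, π = 20% (20 true in each period) | N = 120, π = 50% (60 true in each period) | Ratio |
|---|---|---|---|
| 90% / 90% | 18 vs 18 | 54 vs 54 | 1.00 |
| 90% / 60% | 18 vs 12 | 54 vs 36 | 0.67 |
| 90% / 40% | 18 vs 8 | 54 vs 24 | 0.44 |
| 60% / 90% | 12 vs 18 | 36 vs 54 | 1.50 |
| 40% / 90% | 8 vs 18 | 24 vs 54 | 2.25 |

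The ratio does not depend on N or π. With no change in practice it runs from 0.44 to 2.25 over this range. A proportion of respondents removes the effect if providing and non-providing clinicians respond at the same rate: (N × π × r) / (N × r) = π. If those rates differ, some bias remains.

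**2. Which surveys can represent which period.** Assume that item 4 uses the past-year window printed for item 3, and use the site dates in SAP 3.3.6.

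- A survey at the end of the BEP looks back over about the whole 365-day BEP.
- A survey at the start of the IFEP looks back over about 183 days of the BEP and 182 days of the IF phase (184 and 181 at the two COVID-paused sites), and no IFEP days.
- A survey at the end of the IFEP covers the IFEP almost fully at two sites. At the two paused sites it misses about the first 456 − 365 = 91 and 461 − 365 = 96 days.

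On that assumption, the late-BEP and late-IFEP waves roughly match their periods and the middle wave does not.

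**3. Whether the EHR count covers comparable time.** SAP 7.7 summarises it over the entire BEP and the entire IFEP. The BEP is 365 days at every site. The IFEP is 365 and 367 days at the two unpaused sites, and 456 and 461 calendar days at the two paused ones. The pauses ran from 13 March to 10 June 2020 (89 days) and from 3 March to 6 June 2020 (95 days). Net of the pause, the IFEPs are 456 − 89 = 367 and 461 − 95 = 366 days. Counting only days open to enrolment makes the windows nearly equal. Using all calendar days gives the two paused IFEPs an extra 91 and 96 days in which new clinicians can enter the count.

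**The case against.** **The protocol does not require ED records here.** This is correct. Protocol 12.13 describes secondary data as coming from face-to-face interviews with ED providers and patients. The provider count from ED records in Protocol 8.1 belongs only to the alternative computation of the primary outcome. A reader might infer that the SAP departs from the protocol; it does not.

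**The timing complaint rests on text that is not shown.** This also stands. The item 4 question and its recall window are not in the documents, and nothing says that the survey at the start of the IFEP supplies the IFEP value. A timing mismatch is not established. The remaining point is narrower: the SAP does not say which wave is used.

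**The 25-30 figure is not a ceiling.** Protocol 12.3 gives it as providers engaged in IF activities and evaluation, not as a survey sample, and Protocol 6.4 includes all credentialed ED prescribers. It should not be read as a cap on the count.

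**The EHR count measures something else.** This stands in part. The Table 20 row has no referral element and is not limited to enrolled patients. It is shown as site-by-period totals, which do not supply the provider-level training time that the protocol's offset needs. This argues for reporting both measures. It does not cure the survey count's dependence on who answered.

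**The record-based comparison will be reported anyway.** It will, and SAP 4.2.2 also summarises the number completing each survey by site. Neither is tied to item 4, so the named outcome would still be the raw survey count.

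**Conclusion.** Item 4 as defined cannot separate a change in the number of clinicians providing BUP from a change in survey response. That follows from the source form, the survey population and the absence of a denominator, and it needs no assumption about response rates. The size does need assumptions: over response rates of 40% to 90%, the ratio with unchanged practice runs from 0.44 to 2.25.

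A reader might conclude that the measure favours IF, because clinicians engaged by IF are more likely to answer. That is plausible, but the documents give no response rates, and lower response after IF would push the result the other way. The direction of bias is not established.

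The consequence is limited. This is one of eight secondary implementation outcomes, and SAP 9.0 treats secondary findings as hypothesis-generating. The primary implementation outcome is scored from the ED Visit Review form and is unaffected. The change is still worth making, because a better-suited count is already in hand.

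**What to change.** Amend SAP 7.6.1, item 4, as follows.

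1. Make the between-period comparison on the EHR-abstracted number of unique ED clinicians administering or prescribing BUP, by site, over equal lengths of enrolment time in the BEP and IFEP. At the two paused sites, leave out the pause. Equal windows are safer than a per-day rate, because a count of distinct clinicians need not grow in proportion to time.
2. State that this count does not confirm referral and is not limited to enrolled patients.
3. Report the ICH self-report beside it as a proportion of ED respondents at the late-BEP and late-IFEP surveys, not as a raw count. Print the question, the recall window and the number of respondents.
4. State that the survey at the start of the IFEP is not used as the IFEP value.

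The cost is mainly SAP wording. The documents do not say whether the compiled EHR file holds dates or only period totals; if only totals, the two paused sites would need to recount for the shorter window. The main loss is the referral component in the EHR comparison. As tabulated, 4 sites × 2 periods gives 8 counts, so the offset for time since training would also go unless provider-level data are available.
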